
Major Secondary^{a,b} To assess whether mirikizumab induction dosing is superior to placebo with respect to an early, clinically meaningful response
 
To assess whether the mirikizumab induction dosing is superior to placebo with respect to clinically meaningful response and the highest levels of clinical response
 
To assess whether mirikizumab induction dosing is superior to placebo with respect to body surface area (BSA) affected by psoriasis
	
At Week 4:
 
 Proportion of patients achieving a 75% improvement in PASI (PASI 75) 
At Week 16:
 
 Proportion of patients achieving PASI 75 Proportion of patients achieving a 100% improvement in PASI (PASI 100) 
At Week 16:
 
 Proportion of patients with $\leq 1\%$ of BSA with psoriasis involvement

Objectives	Endpoints

To assess whether mirikizumab induction dosing is superior to placebo with respect to patient-reported outcomes
 
To assess whether 250 mg mirikizumab Q8W and 125 mg mirikizumab Q8W maintenance dosing is superior to placebo with respect to maintenance of a high level of clinical response
	
At Week 16:
 
 • Proportion of patients with a PSS symptoms score of 0 (free of itch, pain, stinging, and burning) in those with a PSS symptoms score ≥ 1 at baseline. • Proportion of patients achieving a DLQI total score of (0,1) with at least a 5-point improvement (reduction) from baseline in patients with a baseline DLQI total score ≥ 5 
At Week 52:
 
 • Proportion of patients maintaining clinical response (PASI 90) after re-randomization at the start of the randomized withdrawal period

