5.4. Scientific Rationale for Study Design

This study will examine the effects of 16 weeks of double-blind dosing (1 dose regimen of mirikizumab versus placebo) during the Induction Period. The selection of placebo as a comparator is justified on the basis that the most robust evaluation of efficacy can be made versus placebo treatment, and the duration of the 16-week primary evaluation is sufficiently short for patients to receive placebo without lasting adverse effects.

In the Maintenance with Randomized Withdrawal Period, double-blind dosing with 250 mg mirikizumab Q8W, 125 mg mirikizumab Q8W, or placebo will be evaluated. Patients who were not responders to LY3074828 in the Induction Period will be switched to 250 mg mirikizumab Q8W in the Maintenance Period so that partial or slow responders may remain in the study beyond Week 16, thus maintaining the study blind while patients continue to receive longer-term treatment with mirikizumab. The purpose of this study period is to determine the optimal dosing level for the maintenance of response or remission, to evaluate relapse or rebound following treatment withdrawal, and to measure response to retreatment following relapse.

The Post-Treatment Follow-up Period is included for safety monitoring following the last study visit for patients who do not enroll in Study AMAH or who discontinue early from Study AMAK.

The dose justification for mirikizumab is outlined in Section 5.5, and the study blind will be maintained as described in Section 7.3.

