Results from Study AMAF also suggest that additional dosing, if given during the Induction Period, might have further improved efficacy at Week 16. This suggestion is based on incremental benefits observed following a third dose administered to Week 16 nonresponders, when assessed within 4 week to 8 weeks of that dose. Model-based analyses and simulations indicate that 250-mg doses administered at Weeks 0, 4, 8, and 12 (1000 mg total) will maximize efficacy at the end of the 16-week Induction Period.

A dosing regimen of 250 mg SC Q8W during the Maintenance Period is expected to maintain or further enhance the efficacy achieved at the end of the Induction Period. The 250-mg dose is expected to achieve exposures and efficacy that are not distinguishable from that observed with 300-mg dosing. A second maintenance dosing regimen of 125 mg Q8W SC was chosen to determine whether efficacy could be maintained with a lower dosing regimen. This second dosing regimen is expected to result in mirikizumab concentrations that have, in individual subjects, minimal overlap with the concentrations produced with the 250 mg mirikizumab Q8W SC regimen.

CCI

6. Study Population

Prospective approval of protocol deviations to recruitment and enrollment criteria, also known as protocol waivers or exemptions, are not permitted.

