10.1. Sample Size Determination

Approximately 500 patients will be randomized at a 4:1 ratio in the blinded Induction Period to receive 250 mg mirikizumab or placebo SC at Weeks 0, 4, 8, and 12. Stratified block randomization will be performed with the following stratification factors: previous exposure to biologic therapy (yes/no), body weight (<100 kg or ≥100 kg), and geographic region (North America or Other).

There are multiple primary endpoints in this study: sPGA (0,1) and PASI 90 at Week 16. The assumed sPGA (0,1) responses are 70% for the mirikizumab arm and 5% for the placebo arm. The assumed PASI 90 responses are 70% for the mirikizumab arm and 3% for the placebo arm. These assumptions are based upon the results of the mirikizumab Phase 2 Study AMAF (Reich et al. 2017b) and review of historical clinical studies in psoriasis (Langley et al. 2014; Gordon et al. 2016; Blauvelt et al. 2017; Papp et al. 2017; Reich et al. 2017a).

With a total sample size of 500 patients, randomizing 400 patients to the mirikizumab arm and 100 patients to the placebo arm, this study has power of >95% for testing superiority of mirikizumab to placebo based on a 2-sided chi-square test with alpha of 5% on sPGA(0,1). It also provides a power of >95% for testing superiority of mirikizumab to placebo on PASI 90 based on a 2-sided chi-square test with alpha of 5%.

In order to account for multiple testing for the comparisons of 2 mirikizumab groups against the placebo group in the Maintenance Period, a 2-sided chi-square test at the 0.025 level is assumed. Assuming 70% of the mirikizumab patients are re-randomized in the Maintenance Period at Week 16 (Visit 7) at a 1:1:1 ratio to 250 mg mirikizumab Q8W, 125 mg mirikizumab Q8W or placebo, approximately 93 patients will be included in each treatment group. Stratified block randomization will be performed with the stratification factor of body weight at baseline (<100 kg or ≥100 kg). This sample size will provide >95% power to test the difference in the proportion of patients maintaining PASI 90 from Week 16 (Visit 7) after re-randomization at the start of the Maintenance Dosing Period to Week 52 (Visit 16) between each mirikizumab dosing interval and placebo, assuming the proportions of patients maintaining PASI 90 are 80% for 250 mg mirikizumab Q8W, 70% for 125 mg mirikizumab Q8W, and 10% for placebo.

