5.1. Determination of Sample Size

Approximately 500 patients will be randomized at a 4:1 ratio in the blinded Induction Period to receive 250 mg mirikizumab or placebo SC at Weeks 0, 4, 8, and 12. Stratified block randomization will be performed with the following stratification factors: previous exposure to biologic therapy (yes/no), body weight (<100 kg or ≥100 kg), and geographic region (North America or Other).

There are multiple primary endpoints in this study: static Physician’s Global Assessment (sPGA) (0,1) and PASI 90 at Week 16. The assumed sPGA (0,1) responses are 70% for the mirikizumab arm and 5% for the placebo arm. The assumed PASI 90 responses are 70% for the mirikizumab arm and 3% for the placebo arm. These assumptions are based upon the results of

the mirikizumab Phase 2 Study AMAF (Reich et al. 2017) and review of historical clinical studies in psoriasis (Langley et al. 2014; Gordon et al. 2016; Blauvelt et al. 2017; Papp et al. 2017; Reich et al. 2017).

With a total sample size of 500 patients, randomizing 400 patients to the mirikizumab arm and 100 patients to the placebo arm, this study has power of >95% for testing superiority of mirikizumab to placebo based on a 2-sided chi-square test with alpha of 5% on sPGA(0,1). It also provides a power of >95% for testing superiority of mirikizumab to placebo on PASI 90 based on a 2-sided chi-square test with alpha of 5%.

In order to account for multiple testing for the comparisons of 2 mirikizumab groups against the placebo group in the Maintenance Period, a 2-sided chi-square test at the 0.025 level is assumed. Assuming 70% of the mirikizumab patients are re-randomized in the Maintenance Period at Week 16 (Visit 7) at a 1:1:1 ratio to 250 mg mirikizumab Q8W, 125 mg mirikizumab Q8W or placebo, approximately 93 patients will be included in each treatment group. Stratified block randomization will be performed with the stratification factor of body weight at baseline (<100 kg or \geq 100 kg). This sample size will provide >95% power to test the difference in the proportion of patients maintaining PASI 90 from Week 16 (Visit 7) after re-randomization at the start of the Maintenance Dosing Period to Week 52 (Visit 16) between each mirikizumab dosing interval and placebo, assuming the proportions of patients maintaining PASI 90 are 80% for 250 mg mirikizumab Q8W, 70% for 125 mg mirikizumab Q8W, and 10% for placebo.

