Induction Safety	All randomized patients who received at least 1 dose of study treatment . Safety analyses for the induction period will be conducted on this population.
Re-randomized Maintenance ITT	All Induction ITT patients who received at least 1 induction dose of study treatment and have been re-randomized at Week 16. Efficacy and health outcomes analyses for the maintenance period will be conducted on this population.
Re-randomized Maintenance Safety	All Induction ITT patients who received at least 1 induction dose of study treatment, have been re-randomized at Week 16 and have received at least 1 maintenance dose . Safety analyses for the maintenance period will be conducted on this population.
Non-re-randomized Maintenance ITT	All Induction ITT patients who received at least 1 induction dose of study treatment, have not been re-randomized at Week 16, and have entered the maintenance period (Table AMAK.6.3). Efficacy analyses for the maintenance period will be conducted on this population.
Maintenance ITT	Pooled re-randomized and Non-re-randomized populations.
Re-randomized Relapsed	All Re-randomized Maintenance ITT patients who relapse during the Maintenance Period and received a 250-mg dose. These patients will be analyzed for recapture of efficacy response.
All Miri Safety	All randomized patients who received at least 1 dose of mirikizumab . Patients who received placebo for the entire study are not included.
Induction PPS	All randomized patients who do not have important protocol deviations excluded from per protocol analysis (IPDPP) in the induction period. IPDPP are described in a separate document: “The AMAK Trial Issues Management Plan.” These patients will be used as a sensitivity analysis for the primary endpoints only.

Abbreviations: ETV = early termination visit; ITT = intent-to-treat; PPS = per protocol set.

Table AMAK.6.2. Treatment Groups and Comparisons for Each Study Period and Analysis Population

Study Period	Analysis Population	Treatment Groups	Inferential Comparisons
Induction	Induction ITT Induction Safety Induction PPS	placebo Q4W; 250 miri Q4W	250 miri Q4W vs. placebo Q4W
Maintenance	Re-randomized Maintenance ITT; Re-randomized Maintenance Safety	placebo Q8W ^e ; 125 miri Q8W; 250 miri Q8W; Total miri*	125 miri Q8W vs. placebo Q8W; 250 miri Q8W vs. placebo Q8W
	Re-randomized Relapsed	placebo Q8W ^a e; 125 miri Q8W ^a ; 250 miri Q8W ^a ; Total miri*	No comparison

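### The maintenance period is meant to find the optimal dosing level, but the visible plan has no randomized 250 mg versus 125 mg estimate and the sample is not sized to separate the two doses

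*Protocol*

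**What the plan says.** Protocol 5.4 gives the rationale for the re-randomized period: "The purpose of this study period is to determine the optimal dosing level for the maintenance of response or remission". Protocol 5.5 is narrower about the lower dose: "A second maintenance dosing regimen of 125 mg Q8W SC was chosen to determine whether efficacy could be maintained with a lower dosing regimen".

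The formal parts of the plan concern placebo. The major secondary objective at Week 52 asks whether each dose's "maintenance dosing is superior to placebo with respect to maintenance of a high level of clinical response". For the Re-randomized Maintenance populations, the inferential comparisons in SAP Table AMAK.6.2 are "125 miri Q8W vs. placebo Q8W; 250 miri Q8W vs. placebo Q8W". The sample size sections (Protocol 10.1, SAP 5.1) claim more than 95% power for each dose against placebo, with about 93 patients per arm and assumed PASI 90 maintenance rates of "80% for 250 mg mirikizumab Q8W, 70% for 125 mg mirikizumab Q8W, and 10% for placebo".

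Other planned analyses bear on dose without contrasting the two arms:

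- SAP 6.1.4 gives a 95% interval for each arm's crude proportion.
- SAP Table AMAK.6.6 lists time to relapse, time to loss of PASI 90, stability of response and cumulative time in response for the re-randomized population.
- Protocol 10.3.5 describes graphical and model-based exposure-response analyses, including at Week 52, with details left to a separate PK/PD plan.

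**The concern.** Choosing between two active doses calls for a comparison of those doses. On the planning rates, both doses will almost certainly beat placebo, and two significant placebo tests do not rank them. The report would then show two response rates side by side, each with its own interval, and readers would form their own view of the difference without an interval for it. Re-randomization at 1:1:1 makes the direct contrast available from data that will be collected anyway. The comparison also matters after this trial, because Protocol 5.1.3 says the extension study uses both regimens.

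**Working it through.** **Inputs.** The protocol plans 400 patients on mirikizumab (5.2). Section 10.1 then gives: "Assuming 70% of the mirikizumab patients are re-randomized in the Maintenance Period at Week 16"; 1:1:1 allocation; assumed rates of 80%, 70% and 10%; and for each placebo comparison, "a 2-sided chi-square test at the 0.025 level is assumed". The documents give no alpha for a between-dose test. I assume two-sided 0.05 and show 0.025 as well. No dropout allowance is stated for this period and none is applied.

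**Patients per arm.** 400 × 0.70 / 3 = 93.3, which agrees with the plan's 93.

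**The plan's own power figure.** For rates p1 and p2 with mean p̄ and n per arm, the two-sided chi-square power is approximately Φ[(|p1 − p2| − z·SE0)/SE1], where SE0 = √(2p̄(1 − p̄)/n) and SE1 = √((p1(1 − p1) + p2(1 − p2))/n). At alpha 0.025, z = 2.241.

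- 250 mg vs placebo: SE0 = 0.0730, SE1 = 0.0518; (0.70 − 2.241 × 0.0730)/0.0518 ≈ 10.3, so power exceeds 99.9%.
- 125 mg vs placebo: SE0 = 0.0718, SE1 = 0.0568; (0.60 − 2.241 × 0.0718)/0.0568 ≈ 7.7, so power exceeds 99.9%.

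The stated figure of more than 95% is therefore correct, with a wide margin.

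**The comparison that is not planned, 80% vs 70% with 93 per arm.**

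- SE1 = √((0.16 + 0.21)/93) = 0.0631.
- 95% half-width = 1.96 × 0.0631 = 0.124, so the expected interval around 10 points runs from −2.4 to +22.4 points.
- SE0 = √(2 × 0.75 × 0.25/93) = 0.0635. Power at two-sided 0.05 = Φ[(0.10 − 1.96 × 0.0635)/0.0631] = Φ(−0.39) ≈ 35%. Full enumeration of the Pearson test also gives 35%.
- Power at two-sided 0.025 is 25%.
- For 80% power at two-sided 0.05, about 294 patients per arm would be needed. With 93 per arm and 80% in one arm, the other would have to be about 61%, a gap of about 19 points.

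**Sensitivity to the share re-randomized** (my range; rates held at 80% and 70%, two-sided 0.05):

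| Share re-randomized | Per arm | Half-width | Power |
|---|---|---|---|
| 60% | 80 | 13.3 points | 31% |
| 70% (plan) | 93 | 12.4 points | 35% |
| 80% | 107 | 11.5 points | 39% |
| 90% | 120 | 10.9 points | 43% |

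**What the planned per-arm intervals would show.** 1.96 × √(0.8 × 0.2/93) = 8.1 points and 1.96 × √(0.7 × 0.3/93) = 9.3 points, so about 72% to 88% and 61% to 79%. They overlap, but neither is an interval for the difference.

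**The case against.** The strongest reply is that one sentence of rationale is out of line with an otherwise consistent plan. The objectives, sample size and comparison table agree with one another, and no type I error or stated power is affected. That is correct, and it limits the weight of the point.

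A reader might go further and infer that the trial cannot inform the choice of dose at all, or that the two rates would be reported with no statement of uncertainty. The documents support neither inference. SAP 6.1.4 plans an interval for each arm. Relapse, stability and cumulative response are analysed by arm. Exposure against efficacy is a listed secondary endpoint, and Protocol 5.5 expects little overlap in concentrations between the regimens, so that work would span both doses. This is relevant evidence, but it is indirect. Overlapping per-arm intervals do not quantify a difference, and a model of observed exposure is not a randomized contrast.

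Nor does Protocol 5.5 go unanswered. The 125 mg arm "was chosen to determine whether efficacy could be maintained with a lower dosing regimen", and the 125 mg versus placebo test bears on that. It does not serve the broader purpose in 5.4.

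Two further objections stand in part. First, absence can be claimed only for the visible text: the protocol's exploratory analysis section is redacted, the multiplicity figure is not shown, and the PK/PD plan and supplemental SAP are separate documents. Table AMAK.6.2 is visible, however, and lists only placebo comparisons. Second, an added interval would probably not separate the doses at a true 10-point difference. That is a reason to reword 5.4 as well, and the interval would still show readers how much the data leave open.

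**Conclusion.** The point holds as a mismatch between a stated purpose and the planned analyses. No randomized 250 mg versus 125 mg estimate appears in the visible text, evidence on dose is indirect, and the sample is not sized to separate the doses. The half-width of about 12.4 points rests on the plan's 93 per arm and its assumed 80% and 70%; the 35% power rests also on my assumed two-sided 5% alpha. The placebo comparisons and their power are sound. This is a cheap improvement to make and not a defect in the confirmatory analysis. Nothing here says which dose is preferable.

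**What to change.** Add one estimation-only row to SAP Table AMAK.6.2 for the Re-randomized Maintenance ITT population: 250 mg Q8W minus 125 mg Q8W. Use the common risk difference with 95% interval already specified in SAP 6.1.4, stratified by body weight as in SAP 6.2 and with non-responder imputation. Report it for PASI 90 and PASI 100 at Week 52; PASI 100 is included because 5.4 covers remission, which Protocol 5.1.3 defines as PASI 100. Assign it no alpha, keep it outside the graphical procedure, and state the expected half-width of about 12 points.

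Optionally, give the same contrast at Week 48 before dosing. With 8-weekly dosing from Week 16, that visit ends a dosing interval, whereas Week 52 falls four weeks after the last dose. PASI is already collected at both visits.

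At the next amendment, reword Protocol 5.4 to say that the period tests each dose against placebo and estimates the difference between doses.

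The SAP change needs a few lines and no extra patients, data or alpha. It is best made before the Week 16 lock, when a small sponsor group may gain access to the data, and at the latest before the Week 52 lock. The 5.4 change is a protocol edit and goes to the ethics boards with the rest of the amendment. The stated purpose of the period also becomes more modest.

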5.5. Justification for Dose

The dose levels and regimens selected for this study were based primarily on analyses of interim PK, safety, and efficacy data from the Phase 2 Study AMAF, safety data from other clinical studies evaluating mirikizumab, and nonclinical safety data.

Safety Considerations

Single doses of up to 600 mg IV were evaluated in Study AMAA (healthy subjects and psoriasis patients) and up to 1200 mg IV in Study I6T-JE-AMAD (healthy subjects); no dose-related safety or tolerability issues were observed in either study. Evaluation of the safety data available to date in the ongoing Phase 2 studies in patients with ulcerative colitis (Study I6T-MC-AMAC) and in patients with Crohn's disease (Study I6T-MC-AMAG) that are evaluating higher and more frequent dose regimens of up to 1000 mg IV Q4W for up to 52 weeks has not revealed any difference in the safety profile resulting from these higher exposures.

CCI

No dose-related safety or tolerability issues have been observed in Study AMAF, including in patients who were non-responders and received a third dose of 300 mg SC at Week 16. Although the proposed 250 mg Q4W induction dose regimen for this study is expected to produce modestly higher average concentrations than the highest dose regimen evaluated in

Study AMAF, the safety data collected from completed and ongoing clinical studies and from nonclinical toxicology studies supports the proposed dose regimens.

Efficacy Considerations

In Study AMAF, doses of 30, 100, and 300 mg mirikizumab administered Q8W SC provided significant efficacy relative to placebo, with 100 and 300 mg achieving greater efficacy than 30 mg at Week 16. The 300-mg dose provided the highest efficacy for the primary endpoint at Week 16 (PASI 90) and demonstrated a trend towards providing higher PASI 90 and PASI 100 rates at earlier time points; the 300-mg dose also provided a more durable response following Week 16. Thus, results from Study AMAF indicate that the highest dose (300 mg) provided the greatest efficacy.

Results from Study AMAF also suggest that additional dosing, if given during the Induction Period, might have further improved efficacy at Week 16. This suggestion is based on incremental benefits observed following a third dose administered to Week 16 nonresponders, when assessed within 4 week to 8 weeks of that dose. Model-based analyses and simulations indicate that 250-mg doses administered at Weeks 0, 4, 8, and 12 (1000 mg total) will maximize efficacy at the end of the 16-week Induction Period.

A dosing regimen of 250 mg SC Q8W during the Maintenance Period is expected to maintain or further enhance the efficacy achieved at the end of the Induction Period. The 250-mg dose is expected to achieve exposures and efficacy that are not distinguishable from that observed with 300-mg dosing. A second maintenance dosing regimen of 125 mg Q8W SC was chosen to determine whether efficacy could be maintained with a lower dosing regimen. This second dosing regimen is expected to result in mirikizumab concentrations that have, in individual subjects, minimal overlap with the concentrations produced with the 250 mg mirikizumab Q8W SC regimen.

CCI

6. Study Population

Prospective approval of protocol deviations to recruitment and enrollment criteria, also known as protocol waivers or exemptions, are not permitted.

6.1. Inclusion Criteria

Patients are eligible to be included in the study only if they meet all of the following criteria within the screening period, which is ≤ 28 days prior to the start of study treatment unless otherwise defined:

Type of Patient and Disease Characteristics

- [1] Present with chronic plaque psoriasis based on the investigator-confirmed diagnosis of chronic psoriasis vulgaris for at least 6 months prior to baseline, and meet the following criteria:
 - A. Plaque psoriasis involving $\geq 10\%$ body surface area (BSA) and absolute PASI score ≥ 12 in affected skin at screening (Visit 1) and baseline (Visit 2), and
 - B. sPGA score of ≥ 3 at screening (Visit 1) and baseline (Visit 2).
- [2] Candidate for systemic therapy and/or phototherapy.

Patient Characteristics

[3a] Male patients:

No male contraception required except in compliance with specific local government study requirement.

[3b] Female patients:

Women not of childbearing potential may participate and include those who are:

- A. Infertile due to surgical sterilization (hysterectomy, bilateral oophorectomy, or tubal ligation), congenital anomaly such as mullerian agenesis,
OR
- B. Postmenopausal, defined as:
 - i. A woman at least 50 years of age with an intact uterus, not on hormone therapy, who has had either:
 - a. Cessation of menses for at least 1 year,
OR
 - b. At least 6 months of spontaneous amenorrhea with a follicle stimulating hormone >40 mIU/mL,

OR

- ii. A woman 55 years or older not on hormone therapy, who has had at least 6 months of spontaneous amenorrhea,

OR

- iii. A woman at least 55 years of age with a diagnosis of menopause prior to starting hormone replacement therapy.

Women of childbearing potential:

- A. Must test negative for pregnancy prior to initiation of treatment as indicated by a negative serum pregnancy test at the screening visit followed by a negative urine pregnancy test within 24 hours prior to exposure.
- B. Must agree to either remain abstinent, if complete abstinence is their preferred and usual lifestyle, or remain in same-sex relationships, if part of their preferred and usual lifestyle, without sexual relationships with males. Periodic abstinence (for example, calendar, ovulation, symptothermal, post-ovulation methods), declaration of abstinence just for the duration of a trial, and withdrawal are not acceptable methods of contraception.

OR

Must use 2 effective methods of contraception for the entirety of the study. Abstinence or contraception must continue for 12 weeks following completion of investigational product administration.

- i. Two effective methods of contraception (such as male or female condoms with spermicide, diaphragms with spermicide or cervical sponges) will be used. The patient may choose to use a double-barrier method of contraception. Barrier protection methods without concomitant use of a spermicide are not a reliable or acceptable method. Thus, each barrier method must include use of a spermicide. It should be noted that the use of male and female condoms as a double-barrier method is not considered acceptable due to the high failure rate when these methods are combined.
- ii. Of note, one of the two methods of contraception may be a highly effective (less than 1% failure rate) method of contraception (such as combination oral contraceptives, implanted contraceptives or intrauterine devices).

When local guidelines concerning highly effective or effective methods of birth control differ from the above, the local guidelines must be followed.

- [4] Are at least 18 years of age at the time of screening.
- [5] Have adequate organ function, including:
- A. Hematology:
 - i. Absolute neutrophil count $\geq 1.5 \times 10^9/L$ ($\geq 1.5 \times 10^3/\mu L$ or ≥ 1.5 GI/L),
 - ii. Platelet count $\geq 100 \times 10^9/L$ ($\geq 100 \times 10^3/\mu L$ or ≥ 100 GI/L),
 - iii. Hemoglobin level ≥ 10.0 g/dL (≥ 100 g/L),
 - iv. Lymphocyte count > 500 cells/ μL ($> 0.50 \times 10^3/\mu L$ or > 0.50 GI/L),
 - v. Total white blood cell count $\geq 3.0 \times 10^9/L$ ($\geq 3.0 \times 10^3/\mu L$ or ≥ 3.0 GI/L).
 - B. Chemistry:
 - i. Serum creatinine $\leq 2x$ the upper limit of normal (ULN),
 - ii. Alanine aminotransferase (ALT) $\leq 2x$ ULN,
 - iii. Aspartate aminotransferase (AST) levels $\leq 2x$ ULN,
 - iv. Total bilirubin level $< 1.5x$ ULN (patients with Gilbert's syndrome must have serum direct bilirubin < 1.5 mg/dL or < 25.7 $\mu\text{mol/L}$),
 - v. Alkaline phosphatase (ALP) $< 1.5x$ ULN.

(Note: The tests for AST and ALT may be repeated once within a week if the initial response exceeds this limit, and the repeat value may be accepted if it meets this criterion. Other laboratory tests should not be repeated unless there is a technical error or clinical reasons to believe a result may be erroneous, and requires approval by the Eli Lilly and Company [Lilly]-designated medical monitor.)

- [6] Are reliable and willing to make themselves available for the duration of the study and are able and willing to follow study procedures, including use of electronic device for recording of data.

Informed Consent

- [7] Have given written informed consent as a legal adult according to local regulations.

